10.2 Serious Adverse Experiences (SAE)

An SAE is defined as any AE occurring at any dose that results in any of the following outcomes:

- death
- a life-threatening adverse experience
- inpatient hospitalization or prolongation of existing hospitalization
- a persistent or significant disability/incapacity
- a congenital anomaly/birth defect

Other important medical events may also be considered an SAE when, based on appropriate medical judgment, they jeopardize the participant or require intervention to prevent one of the outcomes listed.

10.2.1 Serious Adverse Experience Reporting

The study site will document all SAEs that occur (whether or not related to study drug) per UCSF CHR Guidelines. The collection period for all SAEs will begin after informed consent is obtained and end after procedures for the final study visit have been completed.

In accordance with the standard operating procedures and policies of the local Institutional Review Board (IRB)/Independent Ethics Committee (IEC), the site investigator will report SAEs to the IRB/IEC

11 DISCONTINUATION AND REPLACEMENT OF PARTICIPANTS

11.1 Early Discontinuation of Study Drug

A participant may be discontinued from study treatment at any time if the participant, the investigator, or the Sponsor feels that it is not in the participant's best interest to continue. The following is a list of possible reasons for study treatment discontinuation:

Participant withdrawal of consent

Participant is not compliant with study procedures

Adverse event that in the opinion of the investigator would be in the best interest of the participant to discontinue study treatment

Protocol violation requiring discontinuation of study treatment

Lost to follow-up

Version #:1.5 Version Date: 8/5/2016 Page 31 of 41

Sponsor request for early termination of study

Positive pregnancy test (females)

If a participant is withdrawn from treatment due to an adverse event, the participant will be followed and treated by the Investigator until the abnormal parameter or symptom has resolved or stabilized.

All participants who discontinue study treatment should come in for an early discontinuation visit as soon as possible.

All participants are free to withdraw from participation at any time, for any reason, specified or unspecified, and without prejudice.

Reasonable attempts will be made by the investigator to provide a reason for participant withdrawals. The reason for the participant's withdrawal from the study will be specified in the participant's source documents Refer to Section 10 for early termination procedures.

12.3 Withdrawal of Participants from the Study

A participant may be withdrawn from the study at any time if the participant, the investigator, or the Sponsor feels that it is not in the participant's best interest to continue.

All participants are free to withdraw from participation at any time, for any reason, specified or unspecified, and without prejudice.

Reasonable attempts will be made by the investigator to provide a reason for participant withdrawals. The reason for the participant's withdrawal from the study will be specified in the participant's source documents. As noted above, participants who discontinue study treatment early (i.e., they withdraw prior to Visit 9) should have an early discontinuation visit. Refer to Section 10 for early termination procedures.

12.4 Replacement of Participants

Participants who withdraw from the study treatment will be replaced.

Participants who withdraw from the study will be replaced.

12 PROTOCOL VIOLATIONS

A protocol violation occurs when the participant or investigator fails to adhere to significant protocol requirements affecting the inclusion, exclusion, participant safety and primary endpoint criteria. Protocol violations for this study include, but are not limited to, the following:

Failure to meet inclusion/exclusion criteria

Use of a prohibited concomitant medication, with the exception of the use of unanticipated nitroglycerin and/or nitrates as part of treatment for cardiovascular emergency.

Failure to comply with Good Clinical Practice (GCP) guidelines will also result in a protocol violation. The Sponsor will determine if a protocol violation will result in withdrawal of a participant.

When a protocol violation occurs, it will be discussed with the investigator and a Protocol Violation Form detailing the violation will be generated. This form will be signed by a

Version #:1.5 Version Date: 8/5/2016 Page 32 of 41

Sponsor representative and the Investigator. A copy of the form will be filed in the site's regulatory binder and in the Sponsor's files.

13 DATA SAFETY MONITORING

Adverse events will be monitored by the Clinical PIs (Drs. [name], [name] and [name]) in real-time. In addition, AEs will be reviewed quarterly in the regularly scheduled quality assurance meetings of UCSF Airway Clinical Research Center, which is attended by Drs. [name], [name], [name] and [name].

14 STATISTICAL METHODS AND CONSIDERATIONS

Prior to the analysis of the final study data, a detailed Statistical Analysis Plan (SAP) will be written describing all analyses that will be performed. The SAP will contain any modifications to the analysis plan described below.

14.1 Data Sets Analyzed

All eligible participants who are randomized into the study and receive at least one dose of the study drug (the Safety Population) will be included in the safety analysis.

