4 STUDY DESIGN

4.1 Study Overview

This is a single center, double-blind, randomized, 2 period crossover trial. We propose a sample size of 30. Following a five-day run-in period, during which participants will self-administer 0.9% normal saline by nebulizer three times per day, each participant will be randomized to receive a nebulized dose of study drug three times per day for seven days of either 20% NAC (active) or 0.9% saline (placebo). Following a 28-day washout period, participants will be switched to the alternate group for 7 days of treatment. Participants will be assigned to the treatments in random order. Evaluations will be taken at baseline, end of run-in, start of second treatment period, and at the end of each 7-day treatment period.

Screening data will be reviewed to determine participant eligibility. Participants who meet all inclusion criteria and none of the exclusion criteria will be entered into the study.

The following treatment regimens will be used:

- Experimental treatment of NAC 20%
- Placebo treatment of 0.9% saline

Total duration of participation will be nine weeks. Total duration of the study is expected to be 2 years.

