7 STUDY TREATMENTS

7.1 Method of Assigning Participants to Treatment Groups

Up to 30 eligible patients will be randomly assigned to receive either the experimental treatment (20% NAC) or the placebo treatment (0.9% saline) during period 1 in a 1:1 ratio using a SAS-based computer-generated randomization scheme developed by the study data manager. The investigational pharmacy, who will supply the prepared study medication packets, will complete a randomization worksheet at the end of run-in and log group assignment. This log will be shared with investigators upon study completion or in the event of a serious safety concern.

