14.4 Analysis of Secondary Endpoints

As a secondary outcome, we will include an analysis that examines the change associated with the 7-day treatment with 0.9% saline. Our secondary analysis is to determine the characteristics of participants that respond to NAC. We will classify participants in four groups based on their post-bronchodilator FEV1 in response to NAC. FEV1 of 0-4% change will define non-responders and FEV1 of 5-9%, 10-14%, or > 15% will define the 3 categories of responders. We will examine NAC responders and non-responders to determine if baseline CT mucus scores, lung function measures, or sputum G' measures predict treatment response. We will construct ROC curves to determine the CT score that predicts NAC response thereby identifying a CT biomarker for future thiol saccharide trials. In addition, we will examine how the CT mucus score changes with NAC treatment using a subset of the participants following second period treatment. Finding a decrease in CT score in the 20% NAC group compared to the placebo group will provide support for

 our hypothesis that NAC improves lung function by decreasing intraluminal mucus. Other analyses will be to examine the effects of treatment on sputum elasticity (G').

Safety and tolerability data will be summarized by treatment group.

Adverse event rates will be coded by body system and MedDra classification term. Adverse events will be tabulated by treatment group and will include the number of patients for whom the event occurred, the rate of occurrence, and the severity and relationship to study drug.

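### Section 14.1 limits the Safety Population to eligible participants, so read literally a randomized, dosed participant later found ineligible is left out of the adverse-event rates

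*Combined protocol and SAP*

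**What the plan says.** Section 14.1 (Data Sets Analyzed) gives the only definition of an analysis set in the document. The safety analysis will include "All eligible participants who are randomized into the study and receive at least one dose of the study drug (the Safety Population". That sets three conditions: eligible, randomized, and at least one dose.

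The meaning of eligibility comes from section 4.1: "Participants who meet all inclusion criteria and none of the exclusion criteria will be entered into the study". Section 7.1 uses the same word at randomization: "Up to 30 eligible patients will be randomly assigned to receive either the experimental treatment (20% NAC) or the placebo treatment (0.9% saline".

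Section 12 (Protocol Violations) lists "Failure to meet inclusion/exclusion criteria" as a violation and adds: "The Sponsor will determine if a protocol violation will result in withdrawal of a participant". It does not say what happens to such a person in the analysis.

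Section 14.4 says: "Safety and tolerability data will be summarized by treatment group". It then tabulates adverse events by number of patients and rate, and names no population of its own.

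**The concern.** A safety set is normally defined by exposure: whoever took the drug is counted. Here it is also defined by eligibility, in a protocol that expects some eligibility failures.

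This matters because some exclusions in section 6.3 exist to protect participants: intolerance to study medications, carbamazepine use, and angina with a PRN nitroglycerin or nitrite plan. A person dosed in breach of one of these is someone whose experience a safety table ought to show. Exclusion 2 also rests on the investigator's opinion about safety or data quality. If eligibility were reconsidered after an event, that opinion could decide whether the event is counted. The documents do not say that eligibility is reassessed in this way, but the definition does not guard against it.

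With about 30 participants, one person can decide whether an event appears in the table at all.

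**Working it through.** The plan states no figure on this point, so there is nothing to reproduce. The check is mainly textual, with a short illustration of size.

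**Text**

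1. Section 14.1 makes eligibility a condition of the Safety Population, alongside randomization and dosing.
2. Section 4.1 ties entry to meeting every inclusion criterion and no exclusion criterion. A person who fails one is not eligible in that sense.
3. Section 12 anticipates that such people may be found in the study. Withdrawal is at the Sponsor's discretion, so an ineligible person may also stay in and go on being dosed.
4. Nothing in section 12, 14.1 or 14.4 says that a dosed but ineligible person is kept in the safety analysis.
5. Taking 1 to 4 together, the literal definition leaves that person out.
6. Collection of events is separate. Adverse events are captured throughout the study (8.1.15). Section 10.2.1 says: "The study site will document all SAEs that occur (whether or not related to study drug". Real-time and quarterly review (13) and ongoing committee review of serious events (14.5) are not limited by eligibility. The restriction therefore affects the analysis set and its rates, not the record of events.

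**Size (illustration only)**

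Inputs: planned N = 30 (14.6). The number of ineligible dosed participants, k, is an assumption, since the documents give none. Assume also that all 30 receive the treatment in question, that each of the k people has the event, and that nobody else does. Intervals are Clopper-Pearson 95%. For 0 of m, the upper limit is 1 − 0.025^(1/m).

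| k | All randomized and dosed | Literal 14.1 set |
|---|---|---|
| 1 | 1/30 = 3.3% (0.1% to 17.2%) | 0/29 = 0% (upper limit 11.9%) |
| 2 | 2/30 = 6.7% (0.8% to 22.1%) | 0/28 = 0% (upper limit 12.3%) |
| 3 | 3/30 = 10.0% (2.1% to 26.5%) | 0/27 = 0% (upper limit 12.8%) |

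This is the extreme case. If three people have the event and one of them is ineligible, the rate goes from 3/30 = 10.0% to 2/29 = 6.9%. If the ineligible person has no event, it goes the other way, from 3/30 = 10.0% to 3/29 = 10.3%. The direction depends on the risk of the person left out.

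**How far an event could vanish**

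Section 2.1 quotes nausea at 2-7% and vomiting at 9-12%. Suppose two of 30 are left out and the other 28 carry the quoted rate independently. The chance that none of the 28 has the event is (1 − p)^28:

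- p = 2%: 0.98^28 = 57%
- p = 9%: 0.91^28 = 7%
- p = 12%: 0.88^28 = 3%

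Complete disappearance is plausible only for events at the low end of that range.

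**The case against.** The strongest reply is that *eligible* is loose wording. Section 7.1 applies it to everyone to be randomized, and section 4.1 has screening data reviewed before entry, so eligible and randomized may be meant to describe the same people. Section 14.1 says who is included; no sentence orders the removal of someone later found ineligible. This stands as a possible reading. On it, the word is redundant and deleting it loses nothing. On the literal reading, the word causes the omission.

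A second reply is that the detailed SAP can settle the matter, since "The SAP will contain any modifications to the analysis plan described below". That is true, but the text supplied contains no such modification, and section 14.1 is what a later SAP would start from.

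A reader might infer more than the text supports, in three ways:

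- *That the events themselves are lost.* They are not: capture, reporting and monitoring do not depend on eligibility.
- *That rates are necessarily biased downward because those at greatest risk are removed.* Only some criteria are safety-based. Others, such as a CT mucus score above 3, post-bronchodilator FEV1 below 90% of predicted, the age range or the minimum inhaled corticosteroid dose, are not shown to predict harm. Leaving a person out changes numerator and denominator together.
- *That one or two omissions could hide any event in the 2-12% range.* The calculation above shows this is unlikely for vomiting at 9-12%.

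**Conclusion.** The point holds as a minor defect of definition. Read literally, section 14.1 leaves a randomized, dosed, ineligible participant out of the safety analysis set, and no other section puts them back. Understated adverse-event rates are possible because some exclusions are safety-based, but this is not demonstrated. The size depends on an assumed number of ineligible dosed participants; with one who is the only case, 1/30 (3.3%) becomes 0/29. The dosed total may also exceed 30, because withdrawn participants are replaced (12.4) and section 7.5 provides for up to 8 replacements; that would make each person's share slightly smaller. The efficacy analysis is not touched by this definition.

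**What to change.** In section 14.1, delete *eligible* and keep *randomized*. Suggested text: the Safety Population is all randomized participants who receive at least one dose of post-randomization study drug, regardless of eligibility violations, summarized by treatment received in each period.

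Defining the set as everyone who receives a dose of study drug would go too far. Section 9.3 dispenses the saline run-in supply as study drug at Visit 3, and randomization comes only at Visit 4 (9.4). Without *randomized*, people who never left the run-in could enter the set with no treatment group to be counted in. Specifying a post-randomization dose closes the same gap for anyone randomized whose only doses were in the run-in.

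Listing eligibility violations beside the safety tables would let a reader see whether any events fall in those participants. The cost is one edited sentence, to be carried into the SAP. No new data are needed, and sample size, power and alpha are unaffected.

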14.2 Demographic and Baseline Characteristics

The following demographic variables at screening will be summarized: race, gender, age, height, weight, baseline FEV1, and baseline post-bronchodilator FEV1.

14.3 Analysis of Primary Endpoint

The primary outcome is the % change in FEV1 from the start to the end of the treatment period (either placebo or 20% NAC). The first analysis will be to test the assumption of negligible carryover effects from study period 1 to period 2. We will compare the sum of the outcome values measured in the two periods for each participant across the 2 sequence groups (placebo-20% vs. 20%-placebo) using an unpaired t-test. After no or negligible carryover effect has been confirmed, we will test for the difference in treatment effects between placebo and 20% NAC using a paired t-test.

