14.6 Sample Size and Randomization

We propose a sample size of 30, which will provide us with the power to examine the effect of NAC in a subgroup of individuals with asthma who have CT evidence of intraluminal mucus and to identify the CT mucus score that performs best as a biomarker of treatment response to NAC. Participants will be enrolled if their CT mucus scores are >3.0. To calculate sample size for the one-week treatment period study, we used FEV1 measures from 219 adults with asthma published in Corren et al. NEJM, 2011¹. The authors found that the standard deviation for the change in FEV1 in liters from day 1 to day 7 was 19%. Using a standard deviation of 19 and a two-sided alpha of 0.05, we calculate a sample size of 30 to have 80% power to detect a change in FEV1 of 10% (a reasonable effect size because early studies of Pulmozyme in CF reported a 10% increase in FEV1 at day 3 of treatment).

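### The primary paired t-test on % change in FEV1 is valid but leaves precision unused, because it does not adjust for period baselines the trial already records

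*Combined protocol and SAP*

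**What the plan says.** Section 4.1 describes the design: "This is a single center, double-blind, randomized, 2 period crossover trial". Section 7.1 allocates participants to NAC or placebo "during period 1 in a 1:1 ratio using a SAS-based computer-generated randomization scheme", so about 15 per sequence are planned.

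Section 14.3, repeated in the synopsis, defines the endpoint: "The primary outcome is the % change in FEV1 from the start to the end of the treatment period (either placebo or 20% NAC"). The analysis has two steps. First: "The first analysis will be to test the assumption of negligible carryover effects from study period 1 to period 2". If carryover is judged negligible, "we will test for the difference in treatment effects between placebo and 20% NAC using a paired t-test". Neither place names a baseline covariate or a period term.

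The start-of-period values exist. Sections 9.4 (Visit 4) and 9.7 (Visit 7) list spirometry and post-bronchodilator spirometry ahead of the first supervised dose of each period. Section 14.3 does not say which of the two FEV1 values is the endpoint.

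Section 14.6 justifies the sample size: "The authors found that the standard deviation for the change in FEV1 in liters from day 1 to day 7 was 19" percent. Its conclusion is: "we calculate a sample size of 30 to have 80% power to detect a change in FEV1 of 10" percent. The inputs behind that conclusion are given as: "Using a standard deviation of 19 and a two-sided alpha of 0.05". Section 14 opens by deferring detail to an SAP that may still modify the analysis.

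**The concern.** In a crossover, comparing a person's two end-of-period values already removes that person's stable level. Subtracting each period's starting value brings two further FEV1 readings, with their own noise, into the comparison. That helps when the start-of-period values closely track the end-of-period values, and hurts when they do not. A change score assumes full tracking (slope 1); a model with the baseline difference as covariate lets the data set the slope.

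At stake is precision in a trial of 30 participants planned at 80% power. The adjustment needs no extra visit, test or participant.

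**Working it through.** **Inputs.** From Section 14.6: effect 10, SD 19, two-sided alpha 0.05, N=30, power 80%. From Section 14.3: paired t-test on % change. From Sections 9.4 and 9.7: FEV1 at the start of both periods. Not in the documents, so assumed: r from 0 to 0.9, equal variances of the two differences, and approximate additivity on the percent or log scale.

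**1. Reproduce the plan's figure.** Take 19 as the SD of the paired NAC-minus-placebo difference:

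n = ((1.960 + 0.842) × 19 / 10)² = 28.3, so 29 by the normal approximation. The noncentral t gives 31, and power at N=30 is 79.6%. The stated 30 and 80% therefore reproduce on this reading.

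The text, however, describes 19 as the SD of a single seven-day change. If so, and if the two periods' changes are independent, the paired SD is 19 × √2 = 26.9, power at N=30 is 50.4%, and 59 participants are needed for 80%.

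**2. Variance with and without adjustment.** Let dY and dX be one participant's NAC-minus-placebo differences in end-of-period and start-of-period FEV1, each with variance V and with correlation r.

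- Change score: Var(dY − dX) = V + V − 2rV = 2V(1 − r)
- Baseline-adjusted: V(1 − r²)
- Ratio: (1 − r²) / [2(1 − r)] = (1 + r)/2

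**3. Power at N=30, effect 10.** Noncentral t, with 29 df unadjusted and 27 df adjusted (treatment, period, baseline difference):

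| r | Variance ratio | 19 = paired SD: power (N for 80%) | 19 = one-period SD, independent changes: power (N for 80%) |
|---|---|---|---|
| Unadjusted | 1 | 79.6% (31) | 50.4% (59) |
| 0 | 0.50 | 97.5% (17) | 79.4% (31) |
| 0.3 | 0.65 | 93.1% (21) | 68.4% (39) |
| 0.5 | 0.75 | 89.4% (24) | 62.2% (45) |
| 0.8 | 0.90 | 83.4% (28) | 54.5% (54) |
| 0.9 | 0.95 | 81.4% (30) | 52.3% (56) |

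**4. Simulation check.** With 6,000 trials per setting under the one-period reading, unadjusted power was 49% to 51%. Adjusted power was 78.2%, 66.5%, 60.1% and 52.5% at r = 0, 0.3, 0.5 and 0.8. These fall 1.2 to 2.1 points below the table, which does not charge for estimating the slope in 30 people. The 2-point gain shown at r=0.9 may therefore be nil in practice. Type I error was 4.3% to 5.4% for both methods.

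**5. Carryover.** Suppose NAC given first leaves a 3-point residue in period 2. Only the NAC-first half is affected, so a full shift moves the average by 3/2 = 1.5.

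- Residue equal at the period 2 baseline and end: the change score stays at 10; the adjusted estimate is 10 − 1.5(1 − r), which is 8.5 at r=0 and about 9.3 at r=0.5. Simulation at r=0 gave 10.1 and 8.5.
- Residue at the period 2 baseline but gone by period end: the change score is 10 + 1.5 = 11.5; the adjusted estimate is 10 + 1.5r, which is 10.0 at r=0 and about 10.7 at r=0.5.

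**The case against.** The strongest reply is that a paired t-test on change is a valid, simple test that holds its error rate, and that the benefit of replacing it rests on a correlation no document supplies. FEV1 may well be steadier over seven days than over the roughly five weeks between the period baselines (Day 5 to Day 42). In that case r is high and adjustment adds only 2 to 4 points of power. This stands, and it is why the gain must be shown across the whole range of r.

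A second reply is that adjustment is not free. The Visit 7 baseline is measured after randomised treatment, so adjusting for it can bias the estimate under carryover. This also stands, but it does not favour the change score in general: each method is biased under a different form of carryover (step 5). The plan itself relies on negligible carryover after a 28-day washout.

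A reader might also infer that the trial has only about 50% power because the test is unadjusted. The documents do not support that. The 50% comes from reading 19 as a one-period SD with independent changes, which is a separate question about the sample-size input. If 19 is the paired SD, the planned test has 79.6% power and adjustment only adds margin. Even on the one-period reading, adjustment makes up the shortfall only when r is near 0.

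**Conclusion.** The point holds as a worthwhile improvement in efficiency, not as an error in the test. The planned analysis fixes the baseline slope at 1 and leaves out information already collected. Adjusting for the within-person baseline difference multiplies the variance by (1+r)/2. At N=30 that is worth about 18 points of power at r=0 and 2 at r=0.9 if 19 is the paired SD, or 29 and 2 points if 19 is a one-period SD with independent changes. The gain is large for r up to about 0.3, moderate near 0.5, and slight from 0.8 upward.

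The conclusion rests on equal variances, approximate additivity and negligible carryover. That adjustment never loses precision is a large-sample result; with 30 participants and r near 0.9 the two methods are about level. It would go beyond the documents to claim that adjustment recovers most of any lost power, or that it costs nothing.

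**What to change.** Pre-specify in the SAP, as the primary analysis, a linear model for each participant's NAC-minus-placebo difference in end-of-period FEV1:

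dY = β0 + β1 × sequence (coded +1/−1) + β2 × dX

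Here β0 is the treatment effect, the sequence code carries the period effect, and dX is the participant's NAC-minus-placebo difference in start-of-period FEV1 (Visits 4 and 7). In addition:

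- Choose the percent or log scale in advance.
- State whether FEV1 is pre- or post-bronchodilator, and use the same measure at the start and end of each period.
- State the assumed r with a range, and say whether 19 is the SD of one period's change or of the paired difference.
- Keep the paired t-test on % change as a supporting analysis and carryover sensitivity check.

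A mixed model with a random participant effect and one coefficient for the period-specific baseline is not an equivalent substitute, because that coefficient blends within- and between-person slopes. In simulation at r=0 on the one-period reading (1,500 trials per setting, assumed between-person SD of 20 to 30 points), it had 59% to 67% power, against 77% to 79% for the baseline-difference model.

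The cost is SAP wording, one decision on which FEV1 is meant, and two degrees of freedom (27 instead of 29). The adjusted estimate is also exposed to carryover that persists equally through period 2. The change should be fixed before final data are analysed, so that the choice of method cannot depend on the result.

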STATISTICS Primary Analysis Plan	The primary outcome is the % change in FEV1 from the start to the end of the treatment period (either placebo or 20% NAC). The first analysis will be to test the assumption of negligible carryover effects from study period 1 to period 2. We will compare the sum of the outcome values measured in the two periods for each participant across the 2 sequence groups (placebo-20% vs. 20%-placebo) using an unpaired t-test. After no or negligible carryover effect has been confirmed, we will test for the difference in treatment effects between placebo and 20% NAC using a paired t-test.	
Rationale for Number of Participants	We propose a sample size of 30, which will provide us with the power to examine the effect of NAC in a subgroup of individuals with asthma who have CT evidence of intraluminal mucus and to identify the CT mucus score that performs best as a biomarker of treatment response to NAC. Participants will be enrolled if their CT mucus scores are >3.0. To calculate sample size for the one-week treatment period study, we used FEV1 measures from 219 adults with asthma published in Corren et al. NEJM, 2011¹. The authors found that the standard deviation for the change in FEV1 in liters from day 1 to day 7 was 19%. Using a standard deviation of 19 and a two-sided alpha of 0.05, we calculate a sample size of 30 to have 80% power to detect a	

Version #:1.5 Version Date: 8/5/2016 Page 9 of 41

change in FEV1 of 10% (a reasonable effect size because early studies of Pulmozyme in CF reported a 10% increase in FEV1 at day 3 of treatment).
1

Version #:1.5 Version Date: 8/5/2016 Page 10 of 41

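### The primary test is conditional on carryover being confirmed negligible, but the plan gives no rule for confirming it, about 15 per sequence is too few at margins near 10 points, and no primary analysis is stated if it fails

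*Combined protocol and SAP*

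**What the plan says.** Section 14.3, repeated in the synopsis, sets an order of analysis. It begins: "The first analysis will be to test the assumption of negligible carryover effects from study period 1 to period 2". The method is an unpaired t-test: "We will compare the sum of the outcome values measured in the two periods for each participant across the 2 sequence groups". Then: "After no or negligible carryover effect has been confirmed, we will test for the difference in treatment effects between placebo and 20% NAC", by a paired t-test.

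Neither place gives the carryover test an alpha, an equivalence margin or an interval rule. Neither says what the primary analysis is if carryover is not found negligible. The only alpha in the plan belongs to the sample size in section 14.6: "Using a standard deviation of 19 and a two-sided alpha of 0.05, we calculate a sample size of 30 to have 80% power", for a 10% change in FEV1.

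The design's protection against carryover is in section 4.1: "Following a 28-day washout period, participants will be switched to the alternate group for 7 days of treatment". Section 14 promises a later, fuller analysis plan: "The SAP will contain any modifications to the analysis plan described below".

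**The concern.** The sentence asks the data to establish an absence. A non-significant test can do that only if it would probably have detected a carryover worth worrying about. If it would not, a report that follows the plan to the letter will say carryover was ruled out when the data could not show it.

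The second problem is the failing branch. If the preliminary test is significant, by chance or otherwise, the current text leaves the trial without a primary analysis. Unless the SAP supplies one, the replacement would be chosen with the data in view.

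A smaller matter is that the paired t-test has no period term, although the two periods start differently. Period 1 starts at Visit 4, after this: "Following a five-day run-in period, during which participants will self-administer 0.9% normal saline by nebulizer three times per day". Period 2 starts at Visit 7, after the washout and with no run-in.

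**Working it through.** **Inputs.** N = 30, SD 19, effect 10 points, two-sided alpha 0.05, power 80% (section 14.6). Allocation is 1:1 (section 7.1), so 15 per sequence. Withdrawals are replaced (section 12.4), so 30 is used as it stands. Assumed, because the plan does not give them: a 0.05 level for the carryover test, and the correlation rho between a participant's two period changes.

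**1. The plan's own figure.** The paired formula gives n = (19 × (1.960 + 0.842) / 10)² = 28.3, so 29. The exact t calculation gives 31, with 79.6% power at 30. The stated 30 reproduces, but only with 19 as the SD of the within-participant difference. Section 14.6 describes something else: "The authors found that the standard deviation for the change in FEV1 in liters from day 1 to day 7 was 19" percent, which is the SD of one 7-day change. Both readings are therefore carried forward; they coincide at rho = 0.5.

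**2. Power of the carryover test.** It compares period sums, 15 v 15, on 28 df.

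- Reading A (19 is the per-period SD): SD of sum = 19 × √(2(1 + rho)).
- Reading B (19 is the SD of the difference): SD of sum = 19 × √((1 + rho)/(1 − rho)).
- 95% CI half-width = 2.048 × SD of sum × √(2/15).
- Power from the noncentral t with noncentrality 10 / (SD of sum × √(2/15)).

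| Reading | rho | SD of sum | Power, 10-point carryover | Half-width |
|---|---|---|---|---|
| A | 0 | 26.87 | 16.6% | 20.1 |
| A | 0.5 | 32.91 | 12.7% | 24.6 |
| A | 0.8 | 36.05 | 11.4% | 27.0 |
| B | 0 | 19.00 | 28.5% | 14.2 |
| B | 0.5 | 32.91 | 12.7% | 24.6 |
| B | 0.8 | 57.00 | 7.5% | 42.6 |

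At a 0.10 level the power range over both readings is 14% to 41%. Under reading B, 80% power against 10 points would need 58 per sequence at rho 0 and 171 at rho 0.5.

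**3. Could an interval rule rescue it?** With zero true carryover and rho from 0 to 0.8, the chance that the 95% CI lies wholly within ±10 points is under 0.1%. For a 90% CI it is at most 1.2%.

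**4. Negative correlation.** At rho = −0.3 under reading B, SD of sum = 19 × √(0.7/1.3) = 13.94. Power rises to 47%, and the half-width is 2.048 × 13.94 × 0.3651 = 10.4 points, still wider than 10.

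**5. Failure by chance.** With zero carryover, a 0.05 test fails in 5% of trials. With equal period variances the sum and the difference are uncorrelated, so if no test followed a failure, power would be 0.95 × 79.6% = 75.6% (rho 0.5). Simulation also gives 75.6%.

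**6. What carryover would do to the estimate.** The outcome is change from each period's own start. A NAC residual equally present at Visits 7 and 8 cancels from an absolute change and nearly cancels from a percentage change. Only a residual that changes between those visits matters. It enters the saline change of the NAC-first half of participants, so it biases the estimate by half the change: upward if the residual fades, downward if it grows.

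As an illustration of size, assume a 10-point effect that decays exponentially and keeps a fraction x per 7 days. The loss between Visits 7 and 8 is 10·x⁴·(1 − x). This is largest at x = 0.8: 10 × 0.4096 × 0.2 = 0.82 points, a bias of 0.41.

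**7. Period term.** With 15:15 and assumed period effects of 2, 5 and 10 points (rho 0.5), paired-t power is 79%, 78% and 71%, against about 79.5% with a period term. There is no bias in either. With an assumed 18:12 split, the paired estimate is off by (18 − 12)/30 × the period effect, that is 0.4, 1.0 and 2.0 points.

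**The case against.** The best defence has four parts.

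*The SAP will settle it.* Section 14 does promise a SAP that may modify the plan, so the missing fallback is a gap in the current text and may yet be filled. But the present text already states a rule, and a promise to add detail does not make that rule workable.

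*Twenty-eight days is ample for a 7-day inhaled treatment.* This largely stands. It is a reason to rely on the washout and say so; it does not make the test informative.

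*The correlation is assumed, and the margin is the reviewer's.* This stands in part. A reader might infer that the data could never confirm negligible carryover, or that the sums carry all the between-participant variation in FEV1. The documents do not support either. The outcome is a within-period change, so stable differences between participants are largely removed before summing, and rho could be low or negative. With a 20-point margin, rho 0 and 19 as the SD of the difference, a 90% CI would fall inside the margin about 76% of the time. That margin is twice the design effect, and the plan states none.

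*The harm is hypothetical.* A reader might infer that the NAC effect will be inflated by several points. A 5-point inflation would need a 10-point residual to survive 28 days intact and then vanish within 7. The documents give no kinetics to support that, and smooth decay gives about 0.4 points at most. Likewise, a reader might infer that the paired t-test is biased for want of a period term. That needs both a period effect and unequal sequences; the plan says 1:1 and does not say whether the list is blocked.

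**Conclusion.** The point holds and should be fixed, with high confidence on three things: *confirmed* and *negligible* are undefined, the test is too weak to confirm anything at a margin near 10 points, and the current text has no primary analysis for the failing branch. Power against a 10-point carryover is 7.5% to 28.5% across both readings of the SD, for rho 0 to 0.8, 15 per sequence and an assumed 0.05 level. A negative correlation would improve this without curing it.

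The drop from about 80% to 76% power applies only if no test follows a failure, which the plan does not say. Nor do the documents support a claim of inflated type I error, because that would depend on a fallback they do not name. Any carryover bias is probably small and could go either way. The missing period term is a minor point and adds nothing to the severity.

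**What to change.** In section 14.3, the synopsis and the SAP:

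- Delete the carryover precondition and the word *confirmed*. State that the design relies on the 28-day washout.
- Report the carryover estimate with its 95% CI, and FEV1 by sequence at Visit 4 (pre-dose), Visit 6 and Visit 7 (pre-dose), descriptively and with no decision attached. The visit-level report is what would make a residual visible; a period term would not remove it.
- Run the primary test whatever the carryover estimate, as one period-adjusted crossover analysis at two-sided 0.05, chosen before unblinding. Either use a two-sample t-test between sequences on each participant's period 1 minus period 2 difference (treatment effect is half the difference in means), or a mixed model with treatment and period fixed and participant random.

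The cost is wording only. All the spirometry is already scheduled. The period term uses about one degree of freedom: 79.5% v 79.6% power at 15:15, or about 78% v 80% if the sequences end 18:12 with no period effect (SD of difference 19). In return it protects precision if there is a period effect, and prevents bias if that coincides with unequal sequences.
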